10.2.4 V3 (6 Weeks +/- 2 weeks): 1st control visit

The investigator will collect information regarding changes in the concomitant medication, AEs and MDDs, if any, about the functional recovery of the treated limb (by the means of the ROM and the WBI when available), and about the bone healing consolidation by X-ray images.

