10.2.5 V4 (6 to 9 Months): bone consolidation

The investigator will collect information regarding changes in the concomitant medication, AEs and MDDs, if any, about the functional recovery of the treated limb (by the means of the ROM and the WBI when available), and about the bone healing consolidation process by X-ray images.

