19 FIRST CONTROL VISIT

19.1 VISIT GENERAL INFORMATION

The descriptive statistic (Mean, SD, Median, Q₁, Q₃, Min, Max) will be shown for the following continuous variable:

- Time from surgery to First control visit (days) (calculated as Date of first control minus date of surgery)

The categorical variable to be described is, N and (%):

- Time from surgery to First control visit (days) within the time windows estimated in the protocol (4-8 weeks)? (Yes / No)

The categorical variables to be described are, N and (%):

- Has the bone reached a satisfactory consolidation? (No / Partially / Yes)
- Comments

The categorical variables to be described are, N and (%):

- Did the patient refer pain at the treated limb ? (Not at all / A little bit / Moderately /Quite a bit /Extremely)
- In case of previous question is not equal to 'Not at all' VAS will be described
- In case of previous question is not equal to 'Not at all' VAS Pain Score according to the patient will be described
- X-ray AP image
- X-ray ML image

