24.1 SATISFACTORY BONE CONSOLIDATION

The categorical variables to be described are:

- Number of Implants that reached a satisfactory bone consolidation according to investigator's opinion in any visit
- Number of patients that reached a satisfactory bone consolidation according to investigator's opinion in any visit or implant

The descriptive statistic (Mean, SD, Median, Q₁, Q₃, Min, Max) will be shown for the following continuous variable:

- Time to full consolidation from surgery (months), per implant, considered at the first visit in which the answer is "Yes" in "Has been reached a satisfactory consolidation?" variables. Calculated as date of first satisfactory consolidation minus date of surgery.

A list will be made to identify possible outliers from the "time to full consolidation from surgery" in order to verify if there are any. In case any outliers descriptive of "time to full consolidation from surgery" will be repeated without the outlier data.

A list with satisfactory bone consolidation variables will be shown.

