24.3 WEIGHT BEARING GRADE

The categorical variables to be described are:

- Number of Implants that reached a Full weight-bearing (FWB) from surgery in any visit
- Number of Patients that reached a Full weight-bearing (FWB) from surgery in any visit or implant

The descriptive statistic (Mean, SD, Median, Q₁, Q₃, Min, Max) will be shown for the following continuous variable:

- Time to Full weight-bearing from surgery (months), per implant, considered at the first visit in which the answer is "Full weight-bearing (FWB)" in "Weight-bearing Protocol" variables. Calculated as date of the first visit of Full weight-bearing minus date of surgery.

A list will be made to identify possible outliers from the "time to full weight-bearing" in order to verify if there are any. In case any outliers descriptive of "time to full weight-bearing" will be repeated without the outlier data.

A list with Weight bearing grade variables will be shown.

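### SAP 24.1 'time to full consolidation' summarises visit dates among implants rated consolidated: its level probably runs months too high, and implants never rated 'Yes' have no value

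*SAP*

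**What the plan says.** SAP 24.1 defines the variable per implant, in months from surgery, "considered at the first visit in which the answer is" 'Yes', and adds "Calculated as date of first satisfactory consolidation minus date of surgery". It is summarised by mean, SD, median, quartiles and range. The summary may be repeated without outliers, but no outlier rule is given.

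The consolidation question (No / Partially / Yes) appears at three visits only: first control (SAP 19.1), bone consolidation (SAP 20.1) and device removal (SAP 21.1). Protocol 10.2.4 to 10.2.6 and Table 10.2 place these at 6 weeks ± 2 weeks, 6-9 months ("V4 (6 to 9 Months): bone consolidation") and 10-18 months. A note to Table 10.2 says the timings are estimated averages of site practice.

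Neither document gives a censoring rule, a Kaplan-Meier or interval-censored method, or a value for an implant never rated 'Yes'. SAP 24.1 reports separately the number of implants and patients that consolidated, with a listing.

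SAP 24.3 builds its second time variable in the same way: "Time to Full weight-bearing from surgery (months), per implant, considered at the first visit in which the answer is" full weight-bearing. Weight-bearing grade is also recorded at discharge (SAP 18.2).

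**The concern.** The visit at which consolidation is first recorded is an upper bound on when it happened. With three widely spaced assessments the bound is loose, and averaging such bounds as if they were event times overstates healing time.

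There is also a selection effect. An implant with no 'Yes' has no date, so the summary describes consolidated implants only and cannot respond to failures.

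A figure in months called time to full consolidation is easily read as speed of healing with this device. The study is meant to support the benefit/risk case for keeping the CE mark (Protocol 5.2), so a descriptive performance figure should mean what its name says.

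**Working it through.** The documents state no consolidation time, so there is no figure to reproduce. Steps 1 and 2 follow from the documents. Steps 3 to 6 rest on assumed healing times or assumed counts.

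**1. Possible values.** One month is taken as 30.4375 days.
- V3: 4 × 7 / 30.4375 = 0.92 to 8 × 7 / 30.4375 = 1.84 months
- V4: 6 to 9 months
- V5: 10 to 18 months

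If visits keep to their windows, no recorded time can lie between about 1.8 and 6 months, or between 9 and 10 months, whenever the bone healed.

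**2. Longest interval before a first 'Yes'.**
- At V4: 9 − 0.92 = 8.1 months
- At V5: 18 − 6 = 12 months

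**3. Effect on level and on differences.** Assumptions: true times log-normal with log-SD 0.4, visits uniform in the windows, and the recorded time equal to the first visit on or after the true time. The true mean is median × exp(0.4²/2), which is 3 × 1.083 = 3.25 and 5 × 1.083 = 5.42 months. Simulated results in months:

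| True median | True mean | Recorded mean | Recorded median |
|---|---|---|---|
| 3 | 3.25 | 7.39 | 7.48 |
| 5 | 5.42 | 8.62 | 7.88 |

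- Excess in the mean: 7.39 − 3.25 = 4.14 and 8.62 − 5.42 = 3.20.
- True difference in means: 5.42 − 3.25 = 2.17. Recorded: 8.62 − 7.39 = 1.23, or 57% of it.
- True difference in medians: 5 − 3 = 2. Recorded: 7.88 − 7.48 = 0.40, or 20% of it.

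**4. Effect of the calendar alone.** In a second simulation (log-SD 0.35, true median fixed at 4 months), V4/V5 were moved from 6/10 to 9/18 months. The recorded mean moves from 6.5 to 9.1 and the recorded median from 6.0 to 9.0, with no change in healing.

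**5. Effect of non-consolidation.** With the same log-SD and true median, and visits uniform in the windows, the share never consolidating was set to 0%, 3%, 10% and 20%. The recorded mean is 7.8 months in all four cases.

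**6. What the alternative shows.** Assume 30 implants with first 'Yes' at V3 in 5, at V4 in 20, and never in 5.
- SAP rule at mid-window dates (1.38 and 7.5 months): (5 × 1.38 + 20 × 7.5) / 25 = 6.28 months on n = 25.
- All implants kept: 5/30 = 17% by V3, 25/30 = 83% by V4 and 83% by V5. The median is known only to lie between V3 (about 1.4 months) and V4 (about 7.5 months).

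**The case against.** The strongest reply is that little depends on this variable. Both efficacy endpoints are percentages (Protocol 6.2, SAP 24). Time to consolidation carries no hypothesis or threshold, and the study is uncontrolled with no sub-group statistics planned (Protocol 12.4). The rule is stated openly. Time among consolidated implants is a legitimate conditional description if labelled as such. All of this stands and limits the weight of the point, but it does not make the label accurate.

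A reader might go further in four ways that the documents do not support:

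- **That failures are hidden.** SAP 24.1 gives counts and a listing, and SAP 19.1, 20.1 and 21.1 tabulate No / Partially / Yes at each visit. These sections also give actual times to each visit, so the calendar is visible too. Failures are absent only from the time summary, and even that is inferred from the lack of a rule.
- **That the reported mean is simply set by the calendar.** In step 3 it keeps over half of a true difference. Only the median is nearly insensitive.
- **That the figure will be tested against a published healing time.** The documents' only literature benchmark concerns adverse events.
- **That the same bias size applies to full weight-bearing.** That variable has an extra assessment at about one week, and the simulation does not cover it.

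The healing distribution is also assumed, and the windows are estimates that are not enforced. Actual dates may fall outside them, but the recorded time is still a visit date.

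**Conclusion.** The point holds as a defect in a supporting descriptive variable. Following SAP 24.1 as written overstates healing time, because each value is the end of an interval that can span about 8 months (V4) or 12 months (V5). Implants never rated 'Yes' have no value. The gap in possible values between about 1.8 and 6 months needs only the protocol windows.

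The size depends on assumed healing times. For true means of 3.3 and 5.4 months the recorded mean is about 3-4 months too high. True differences are attenuated in the mean and almost lost in the median. Neither the percentage endpoints nor the primary safety analysis is affected. SAP 24.3 shares the construction, with the effect there unquantified. The change is worth making because the data are already collected and the cost is small.

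**What to change.** **SAP 24.1.** Replace the time summary with the cumulative percentage of implants consolidated by V3, V4 and V5, over all evaluable implants. If a time is wanted, add an interval-censored estimate, with implants never rated 'Yes' right-censored at their last assessment. If the visit-date summary is kept, rename it 'time to first visit with consolidation recorded, among consolidated implants', and give n and the number excluded.

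**SAP 24.3.** Do the same for full weight-bearing, with cumulative percentages by V2 (discharge), V3, V4 and V5.

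**Cost.** A few SAP lines and one table for each variable, with no new data. Most of the content is already in the per-visit tables; what is missing is a fixed denominator and carrying the first 'Yes' forward. The downside is a coarser summary than a single mean, and with about 30 implants any interval-censored median will be imprecise.

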24.2 MAINTAINED BONE CORRECTION

This analysis will be performed for cases that have indicated: Deformity Correction.

The categorical variables to be described are:

- Number of Implants that according to the investigator is the level of correction maintained until last visit performed
- Number of Patients that according to the investigator is the level of correction maintained until last visit performed

A list with maintained bone correction variables will be shown.

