EFFICACY ENDPOINTS	
The clinical performance of JPS will be assessed by the following efficacy endpoints:
 
 - Percentage (%) of subjects that reached a satisfactory bone consolidation according to investigator's opinion (primary efficacy endpoint); - Percentage (%) of subjects that maintained bone correction alignment according to investigator's opinion until device removal. 					
PLANNED STUDY PERIOD	First Patient in	4Q 2022	Last Patient in	2Q 2023	DB closure	2Q 2024 (anticipated)
STUDY DURATION FOR THE SUBJECT	Provided the study is observational. The estimated time of patient observation period is 18 months.					
SITE(S) / COUNTRY(IES)	1 Investigational Site in Germany					
PATIENTS / GROUPS	
Clinical data to be collected only on patients with a regular indication for JPS as per IFU (no off-label use will be included): the system is intended in pediatric (excluding newborns) and small stature adult (that according investigator judgement the patient's anatomy is deemed suitable for the use of JPS plate). Pediatric patients include infants (greater than 1 month to 1 years of age), children (greater than 1 to 12 years of age), adolescents (greater than 12 to 18 years of age) and appropriate adults (where according to investigator assessment, the JPS plates fit the treated bone anatomy).
					
INCLUSION CRITERIA	
A patient will be eligible for inclusion in the study if:
 
 • had a regular indication for surgical intervention with JPS according to the manufacturer's IFU; • underwent a surgery for bone deformity correction or trauma reconstruction of the lower extremities performed by JPS; • the clinical data registered in her/him patient chart are sufficient to assess the safety and efficacy endpoint of the study (for retrospective patients); 					

	
 • patient (or his/her legally acceptable representative) is capable of understanding the content and is willing to sign the Informed Consent Form (ICF) • patient is willing and able to participate in the data collection and comply with the protocol requirements;

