7.3 Study duration

The follow-up period considered for this study lasts until the second surgery for JPS removal that, with the exception of clinical complications, is usually scheduled between 9 and 18 months after the surgery. (see table 10.2 "Events and Assessments Schedule").

The estimated length of data collection period by the investigator is the time until all data is abstracted from clinical records. The data extraction from clinical record will finish after the plate removal of the last patient is completed.

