8.3 Subject Withdrawal

Subjects must be withdrawn once he/she withdrew his/her consent for participation in the study (applicable for prospective cohort).

In all cases, subjects are withdrawn must be recorded in detail in the eCRF. Should the clinical investigation be discontinued prematurely, all clinical investigation materials (complete, partially completed and empty CRFs) will be retained.

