10. STUDY PROCEDURES

10.1 Description of Procedures

Throughout the pre-study meetings, it was assessed and confirmed that the clinical data collected for the study purpose are part of the standard clinical practice for the participating investigational site. As this is an observational study, there are no change or influence to the normal clinical practice of the investigator and patients, and no interference with the local hospital standard of care guidelines and/or the internal therapeutic protocols set and established at the investigational site.

For retrospective study cohort, who have previously had JPS implemented and follow-up assessment and JPS removal is done, the investigators shall purely collect clinical data from the medical record of the subjects, concerning the screening criteria, the surgery (MD application) and 4 following events: hospital discharge, first post-application control, bone consolidation assessment and device removal. Data from patients observation are collected according to the site practice. Please note that the term "Visit" and "Event" are used as synonyms to indicate the steps collected by this observational study.

Patients from the prospective cohort, who have undergone JPS implantation, will be observed in accordance with Table 10.2 or until patient withdrawal.

The patients' data are systematically collected by the investigator in the eCRF provided by Sponsor.

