12.3 Safety and Clinical Performance endpoints

12.3.1 Efficacy endpoints

The clinical performance of JPS will be assessed by the following efficacy endpoints:

- percentage (%) of subjects that reached a satisfactory bone consolidation (primary efficacy endpoint);
- percentage (%) of subjects that maintained bone correction alignment until device removal (secondary efficacy endpoint).

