13.2 Subject Information and Consent

The aim of the study is to collect clinical data based on medical records for patients treated with the JPS system in the past for whom follow-up assessment and JPS removal is already done (retrospective group) and for patients who has undergone JPS implantation and will have follow-up assessments and JPS removal (prospective group).

All subjects should give informed consent to participate in this study. Prior to being enrolled into the study, each patient (if he/she is adult at the time of the screening visit), or his/her parents/legal representative (if he/she is minor at the time of the screening visit), will be required to give his/her written and dated informed consent to participate the study and to collect and process their clinical data, and to anonymously store the data electronically. Also minors patients will be informed as far as possible by the investigators about the study and will be given an age dedicated informed form. Their willingness or refuse to participate to the study, if expressed, must be taken into consideration by the investigator.

Each patient/parents/legal representative will have the opportunity to discuss the informed consent with the Investigator prior to sign it. The Investigator or his/her designee will inform all patient/parents/legal representative regarding the purpose of the study and the clinical data that will be collected. The Investigator will deliberate that, considering this is an observational Study, there are no foreseeable risks resulting from study participation as well as potential benefits that may result from participating in the study.

Each patient/parents/legal representative will be informed by the Investigator that he/she is free to refuse to participate in the study and, if he/she choose to participate, that he/she may withdraw from the study at any time without providing reasons. In addition, the patient/parents/legal representative will be informed that, in some necessary cases, the Investigator may prematurely terminate their participation providing an appropriate reason.

The Investigator will provide the patient/parents/legal Representative with contact details in case they need further information after ICF signature.

Each patient/parents/legal representative will be informed that his/her medical records will be subjected to review by the Sponsor representatives, and may be subjected to review for the

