24 SECONDARY OBJECTIVES

The secondary objective of the study is to evaluate the clinical performance of JPS within the scope of its intended purpose, when used according to the manufacturer IFU on a representative population of subjects and users.

In order to fulfill these objectives the clinical performance of JPS will be assessed by the two following efficacy endpoints:

- percentage (%) of subjects that reached a satisfactory bone consolidation according to investigator's opinion;
- percentage (%) of subjects that maintained bone correction alignment according to investigator's opinion until device removal.

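### SAP 24.2 counts correction as maintained up to the last visit performed, while the endpoint runs to device removal, so cases without a removal visit can count as successes

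*SAP*

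**What the plan says.** The endpoint appears in the protocol synopsis as "Percentage (%) of subjects that maintained bone correction alignment according to investigator's opinion until device removal". Protocol 6.2 and 12.3.1 and SAP sections 7 and 24 also carry it to device removal.

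SAP 24.2 restricts the analysis to deformity corrections and says what is counted: "Number of Patients that according to the investigator is the level of correction maintained until last visit performed". The line for implants uses the same time point.

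The investigator rates maintenance of correction (No / Partially / Yes) at first control, bone consolidation and device removal (SAP 19.2, 20.2, 21.3). Table 10.2 of the protocol puts these at about 6 weeks, 6–9 months and 10–18 months.

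On follow-up, Protocol 10.1 says that prospective patients "will be observed in accordance with Table 10.2 or until patient withdrawal". Protocol 13.2 describes the retrospective group as patients "for whom follow-up assessment and JPS removal is already done (retrospective group". Protocol 7.3 adds: "The data extraction from clinical record will finish after the plate removal of the last patient is completed". The synopsis predicts 10 % drop-out among at most 40 implant cases. SAP 13 defines evaluable implants by eligibility alone, so a removal visit is not required.

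**The concern.** SAP 24.2 is the only place that turns the endpoint into a count, and it uses a different time point from the definition printed a few lines above it. The last visit performed may be the 6-week control. A case that leaves after that visit with a 'Yes' would appear as a success in a row that readers take to mean maintained to removal.

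This is one of only two efficacy endpoints, in a study meant to support the device's CE mark. A row that mixes cases seen at removal with cases last seen earlier, without showing how many of each, is open to misreading.

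**Working it through.** The plan gives no target, sample size or expected rate for this endpoint, so there is no figure to reproduce. The check is a comparison of texts, followed by an illustration of size.

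**Who can be affected**
- Retrospective cases: no, because removal has already taken place.
- Prospective deformity cases that withdraw before removal: yes, if rated 'Yes' when last seen. A case rated 'Yes' throughout counts as a success whether the rule means the last rating or every rating.
- Prospective cases still in the study at database closure: possibly. The synopsis has the last patient in during 2Q 2023 and anticipates closure in 2Q 2024. If surgery falls in the quarter of enrolment (an assumption; it may be earlier), removal at 18 months falls in 4Q 2024. Against this, Protocol 7.3 and SAP 10 keep extraction open until the last removal.

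**Formulas.** Let N be the deformity cases, m the cases without a removal visit and rated 'Yes', and f the cases not maintained at removal.
- SAP 24.2 rule: (N − f)/N
- Observed at removal: (N − m − f)/(N − m)
- Leavers counted as not maintained: (N − m − f)/N

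The SAP rule exceeds the observed rate by f·m/[N(N − m)] and the third count by m/N.

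**Inputs.** N = 40 is the synopsis maximum, assumed here to be all deformity cases. m = 0.10 × 40 = 4 uses the predicted drop-out, assumed all prospective and all rated 'Yes'. f = 0 and f = 2 are assumptions.

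| f | SAP rule | Observed at removal | Leavers as not maintained |
|---|---|---|---|
| 0 | 40/40 = 100 % | 36/36 = 100 % | 36/40 = 90.0 % |
| 2 | 38/40 = 95.0 % | 34/36 = 94.4 % | 34/40 = 85.0 % |

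For f = 2 the gap to the observed rate is 2 × 4/(40 × 36) = 0.6 point. The gap to the third count is 4/40 = 10 points. Clopper-Pearson 95.2 % intervals for that row are 83.0–99.4 %, 81.2–99.3 % and 70.0–94.3 %.

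If the 4 leavers were instead last rated 'No', they are failures already: with f = 2 the SAP rule gives (40 − 4 − 2)/40 = 85.0 %, and counting leavers as not maintained gives the same. With no leavers all counts agree.

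**Choice of denominator.** A rate over known outcomes would keep leavers rated 'No' (known failures) and drop those rated 'Yes', so exclusion would depend on outcome. Suppose 80 % are maintained to bone consolidation, 90 % of these to removal, and 10 % of those still maintained leave after bone consolidation for unrelated reasons (all assumed).
- True rate: 0.80 × 0.90 = 72.0 %
- SAP rule: 0.80 × (0.90 × 0.90 + 0.10) = 72.8 %
- Known-outcome denominator: 0.80 × 0.90 × 0.90/(1 − 0.08) = 0.648/0.92 = 70.4 %
- Bounds over all cases: 64.8 % to 72.8 %, which contain the true rate

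Here the known-outcome rate is further from the truth than the present rule. If failures came mainly after bone consolidation, the order would reverse.

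**The case against.** The strongest reply is that most of the information is already planned. SAP 21.3 tabulates the rating at removal, SAP 14 gives total and valid percentages, SAP 22 gives exit reasons, and SAP 24.2 includes a listing of the correction variables. The endpoint is secondary and descriptive, and using the last available rating keeps every case in the count. The documents also do not say that data are kept after consent is withdrawn; if they are not, some of these cases would drop out of the count.

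Much of this stands, and it limits the importance of the point. A reader may be able to recover the removal-confirmed count. But none of these items corrects the endpoint row. The two percentage columns do not help there, because an early leaver has a valid last rating and is not missing under the SAP 24.2 rule.

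A reader might infer that the SAP rule overstates the result by about 10 points. The documents do not support that. The 10 points appear only if every leaver is assumed to have lost correction; against cases seen at removal the illustrated gap is 0 to 0.6 point. A reader might equally infer that everyone who stays in the study is safe. The planned closure date makes that too firm, although Protocol 7.3 points that way.

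**Conclusion.** The contradiction is real and unreconciled: five statements of the endpoint run to device removal, and the only counting rule stops at the last visit performed. It can misclassify prospective deformity cases without a removal visit that were rated 'Yes', and no others. The number of such cases is unknown and may be zero, because the documents give neither the prospective/retrospective split nor the deformity/fracture split. The illustrated gaps rest on the assumed 4 leavers among 40 deformity cases, which is a high case since only prospective deformity cases can be lost. With no threshold or test on this endpoint, no study conclusion turns on it. Severity is minor. The finding does not show that the reported percentage will be wrong, or that the change of wording was meant to improve it.

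**What to change.** In SAP 24.2, replace the last-visit time point with device removal. Over all evaluable deformity implants, and separately over patients, report three counts: maintained with a removal evaluation, not maintained, and not assessed to removal.

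Give the percentage maintained to removal over all evaluable deformity cases, with two labelled bounds: not-assessed cases counted as not maintained (numerically the same as that percentage), and not-assessed cases counted as maintained (the present rule). Do not use a denominator that drops only the early leavers rated 'Yes'.

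In the same edit the sponsor should fix three rules that SAP 24.2 leaves open: how 'Partially' counts, how a 'No' followed by a 'Yes' counts, and how a patient whose implants differ is classified (one patient can have more than one implant ID). These are the sponsor's choices and are secondary to the main point.

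The cost is revised wording in one SAP section and one or two extra rows. No new data are needed. The reported percentage may be slightly less favourable.
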